##### **10.4.6.1 Adverse Events (AEs)**

All adverse events recorded during the study will be coded according to the Medical Dictionary for Regulatory Activities (MedDRA) and be graded according to the National Cancer Institute Common Terminology for Adverse Events (NCI CTCAE) v4.03 scale (see [Appendix D](#)).

AEs will be summarized for the following:

- Number (%) of patients with any AE,
- Number (%) of patients with any SAE,
- Number (%) of patients permanently withdrawn from study due to an AE.

All summaries will be presented by treatment group and stratified by type of disorder (e.g. malignant or non-malignant). They will include overall frequency of patients with events as well as frequency of patients with events by primary system organ class and preferred term. A patient will only be counted once within each system organ class and preferred term. For summaries regarding severe or study-drug related AEs, the highest severity or relationship will be considered for each patient per preferred term.

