## 2 SYNOPSIS

Study Identifier(s)	BP-404 EudraCT #2016-003226-16
Aim of the Study	This is a Phase I/II study to evaluate the long-term safety of the infusion of BPX-501 gene-modified T cells after mismatched, T cell-depleted allogeneic transplantation and evaluate disease free survival at 1 and 2 years post-transplant
Study Design	
Open label, multi-centre, non-randomized, non-controlled long-term safety evaluation
 
Follow-up of all patients enrolled on BP-004 and treated with BPX-501 who are beyond Day 180 and have completed or discontinued the parent study.

Study Population	The patient population is identical to BP-004 as it is the long-term follow-up of those patients. Estimated enrolment up to 175 BP-004 patients.
Main Inclusion Criteria	
 
1. Signed written informed consent by the patient or the patient's guardian for children who are minors
 
2. Enrolled on BP-004 protocol, received BPX-501 infusion, completed or discontinued from the study, and are beyond Day 180.
 

Main Exclusion Criteria	
 
1. Lack of parents'/guardian's informed consent for children who are minors
 
2. Withdrawal from BP-004 study prior to BPX-501 infusion.
 

Dosage, Treatment Regimen, Route of Administration	
No BPX-501 infusions will be administered under this protocol.
 
Rimiducid to be given at 0.4 mg/kg weight (intravenous infusion) only in the setting of uncontrolled GVHD.

Locations (e.g. regions)	Italy, Saudi Arabia.
Primary Endpoint(s) with Time Point(s) of Assessment	Overall Survival and incidence of Disease-Free Survival in both malignant and non-malignant patients at 1 year and 2 years post-transplant. Relapse-Free Survival in malignant patients at 1 year and 2 years post-transplant.
Main Secondary Endpoint(s) with Time(s) of Assessment	Long-term safety for a total of 15 years from BPX-501 administration

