**Table 3: Guidance for Adverse Event Reporting**

Event Type	Reporting Period	Additional Requirements
GvHD	All cases of GvHD should be reported regardless of onset date and should	Not applicable

	not be limited to the below AE/SAE reporting period	
AEs (post-IMP)	
 
From the date of BPX-501 infusion until 30 days after administration regardless of causality assessment (including later worsening of events that began during this timeframe).
 
From the date of rimiducid infusion until 30 days after administration regardless of causality assessment.
 
	
 
Report new AEs for up to 15 years if assessed as related to the investigational products BPX-501 and/or rimiducid.
 

SAEs (post-IMP) including Adverse Events of Special Interest*	
 
From the date of BPX-501 infusion until 180 days after administration regardless of causality assessment (including later worsening of events that began during this timeframe).
 
From the date of rimiducid infusion until 30 days after administration regardless of causality assessment.
 
	
 
Report new SAEs for up to 15 years if assessed as related to the investigational products BPX-501 and/or rimiducid.
 
Report diagnosis of any new secondary malignancy regardless of relationship to investigational product for up to 15 years.
 

Pregnancy of patients or partner	
 
12 months after administration of BPX-501 or rimiducid, whichever occurs later.
 
	
 
Report diagnosis of any congenital anomaly in offspring from a study participant or partner for up to 15 years.
 

\* Adverse Events of Special Interest are Grade III-V encephalopathy or neurologic events - these should be reported to the Sponsor expeditiously, irrespective of regulatory seriousness criteria.

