### **9.3 End of Study**

The study will evaluate overall survival and disease-free survival for all patients enrolled at 1 and 2 years post-transplant. Patients will be followed for a total of 15 years after BPX-501 treatment for gene therapy safety events. The study will be closed after the completion of the 15 years of follow-up.

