#### **10.4.6 Safety Analysis**

Safety analysis will investigate the analysis populations over the time period defined as from the infusion date of the respective treatment to study end date.

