6.5.1. Adverse Events

Each verbatim adverse event (AE) term recorded during the study will be mapped to a system organ class and preferred term using MedDRA Dictionary version 18.0.

Study treatment-related adverse events will be defined as the adverse events for which the investigator indicates the relationship to study drug as possible, probable, or definite. Relatedness of AEs for patients treated with rimiducid will be assessed among those patients from the date of first dose of AP1903.

All summaries of AEs will present the number and percent of subjects reported events by system organ class and preferred term. If a subject has multiple occurrences of an AE, the subject will be counted only once for the respective AE category at the SOC or preferred term level.

At a minimum, the following AE tables will be summarized by SOC and preferred term:

- Number and percentage of patients with any AE
- Number and percentage of patients with AEs by maximum severity
- Number and percentage of patients with G3 or higher AEs
- Number and percentage of patients with serious AEs (SAEs)
- Number and percentage of patients with AEs leading to death

Summaries will be presented for all subjects as well as by type of disorder (e.g. malignant or non-malignant). If any of the proposed tables has very limited occurrence, only patient listings may be provided.

At a minimum, the following patient listings will be provided:

- All AEs
- All SAEs
- All AEs leading to death

Specific listings and tables for GvHD, infections, and neurological events will be provided. Neurological events will be categorized relative to basket of preferred terms curated against MedDRA version 21.0. Key coding differences between this list and the MedDRA version used for broader AE coding will be highlighted.

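### The 15-year safety summary is a crude number (%), which understates cumulative incidence of late secondary malignancy and related SAEs when patients are lost

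*Protocol*

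**What the plan says.** The Protocol synopsis gives the main secondary endpoint as "Long-term safety for a total of 15 years from BPX-501 administration", and section 9.3 adds: "Patients will be followed for a total of 15 years after BPX-501 treatment for gene therapy safety events".

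Section 10.4.6 analyses safety "over the time period defined as from the infusion date of the respective treatment to study end date". Within that period, section 10.4.6.1 lists "Number (%) of patients with any AE", "Number (%) of patients with any SAE" and the number (%) withdrawn because of an AE. Its counting rule is: "A patient will only be counted once within each system organ class and preferred term". Section 10.4.6.2 says that deaths, SAEs and AEs leading to discontinuation will be summarised, and names no other measure. Section 10.4.2 is consistent with this: tables of qualitative data show counts, percentages and numbers missing. Section 10.4.6 contains no person-time rate, time-to-event method, censoring rule or competing-risk rule.

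Table 3 sets what is collected late. After the early all-cause windows (30 days for AEs and 180 days for SAEs after BPX-501; 30 days for both after rimiducid), new AEs and SAEs are reported to 15 years only if related to either product. Secondary malignancy is the exception: "Report diagnosis of any new secondary malignancy regardless of relationship to investigational product for up to 15 years".

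The SAP uses the same measure for AEs, "Number and percentage of patients with any AE" (6.5.1). It is written for the parent study BP-004, though it may draw on BP-404 data. It lists no malignancy output and no 15-year safety analysis. Its planned outputs do include time to infection.

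**The concern.** A percentage of patients treated equals the 15-year risk only if each patient is observed until the event, death or year 15. Section 6.1 lets patients withdraw at any time and attend visits as they can, and it provides a category for loss to follow-up. A patient lost at year 4 who develops a malignancy at year 9 may go unrecorded, yet counts in the denominator as event-free throughout.

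The direction of the error is therefore known: downward. It is worst for events that occur late, and section 1 gives delayed events as the reason for follow-up of this length. A reader of the final table could not tell a low risk from incomplete observation. The protocol already uses a suitable method elsewhere: section 10.4.5.4 estimates leukemia relapse by cumulative incidence with a 95% confidence interval and death as a competing risk.

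**Working it through.** The documents give no event, death or loss rate and no precision target for 15-year safety, so there is no planned figure to reproduce. The rates below are assumptions shown over a range.

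**Inputs from the documents.** Horizon 15 years (9.3); up to 175 patients (5.3).

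**Assumed.** Event hazard λ, death hazard μ and loss hazard c are constant. Loss is independent of the event, and no event is reported after loss. A yearly loss of 1%, 3% or 5% is taken as c = 0.01, 0.03 or 0.05. With nothing else happening, 1 − exp(−15c) gives 14%, 36% or 53% lost by year 15.

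**Step 1: formula.** With events possible from year L to T = 15:

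crude = exp(−(μ+c)L) × λ/(λ+μ+c) × [1 − exp(−(λ+μ+c)(T−L))]

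The true cumulative incidence is the same expression with c = 0. Death (μ) is in both, so with c = 0 the two are equal. Only loss separates them.

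**Step 2: true incidence 3%, constant hazard, no deaths.** λ = −ln(0.97)/15 = 0.00203.

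| Yearly loss | λ/(λ+c) | 1 − exp(−15(λ+c)) | Crude | Crude/true | Cases counted of 5.25 (3% of 175) |
|---|---|---|---|---|---|
| 1% | 0.1688 | 0.1651 | 2.8% | 0.93 | 4.9 |
| 3% | 0.0634 | 0.3815 | 2.4% | 0.81 | 4.2 |
| 5% | 0.0390 | 0.5418 | 2.1% | 0.70 | 3.7 |

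Adding death at 1–2% a year, with event hazards of 0.2–0.5% a year, barely moves the ratios: 0.93, 0.81–0.82 and 0.71–0.72.

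**Step 3: events starting at year 5.** λ = −ln(0.97)/10 = 0.00305 keeps the true incidence at 3%. Crude becomes 2.7%, 2.2% and 1.8%. With death at 1–2% a year the ratios are 0.91, 0.75 and 0.62.

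**Step 4: check by simulation** (4,000 runs, N = 175; event hazard 0.5% a year from year 5, death 2%, loss 3%). The true value is 4.00%. Crude averaged 3.02% and Aalen-Johansen 4.04%. In patients, that is about 5.2 counted against 7.0.

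**Step 5: a data cut before year 15.** Assume an event hazard of 0.5% a year, death at 2%, no loss, and follow-up spread evenly over 3–7 years. Crude is 2.34%, the true 7-year value is 3.21% and the true 15-year value is 6.25%. Of the gap of 3.91 points to year 15, 3.04 points (6.25 − 3.21) are time not yet elapsed, which no estimator recovers. The other 0.87 points (3.21 − 2.34) come from unequal follow-up.

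**The case against.** Several stronger readings are tempting, and the documents do not support them.

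- *That 15-year safety will be reported from immature data.* No early BP-404 safety cut is scheduled. Section 10.4.6 runs to study end and section 9.3 closes the study after 15 years. The 1- and 2-year evaluations concern survival endpoints, and the 2-year final analysis in SAP 5.2 is tied to the UK version of BP-004. An early cut would add to the shortfall, but most of that addition would be time not yet elapsed (step 5).
- *That deaths bias the percentage.* They do not. A patient who dies event-free is correctly counted as never having the event.
- *That the whole AE table is affected.* The any-AE line is largely a 30-day all-cause window after BPX-501, and all-cause SAE collection ends at 180 days. Unequal long-term follow-up hardly touches either.
- *That the understatement must be large.* No loss rate is given, and the protocol works to limit loss. Section 6.1 keeps patients with attendance problems on study, follows withdrawn patients for survival and recurrence where possible, and requires three documented telephone attempts, then certified mail or similar where appropriate. Section 9.2.6 asks for later cancers and related SAEs to be reported if the investigator learns of them.

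These measures should shrink the bias. They do not remove it, because awareness after loss is incomplete and the denominator still ignores time at risk. It also remains true that no analysis of secondary malignancy is defined in either document.

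**Conclusion.** The point stands for delayed events collected to year 15: new secondary malignancy of any cause, and SAEs related to BPX-501 or rimiducid. For these, a crude percentage understates cumulative incidence whenever patients are lost and their later events go unreported.

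The size cannot be derived from the documents. Under the stated assumptions, a true 3% would read as 2.8% to 2.1% for yearly loss of 1% to 5%, or 2.7% to 1.8% if events begin at year 5. With no loss and full follow-up of survivors, the error is zero. In absolute terms the constant-hazard cases are between about 0.4 and 1.6 missing cases in 175. This calls for a cheap improvement to the analysis text; it does not put the study's validity in question.

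**What to change.** For secondary malignancy and for related SAEs, add to the analysis plan:

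- Aalen-Johansen cumulative incidence from BPX-501 infusion, with death competing and censoring at last contact, with 95% CI and numbers at risk. Report it at 2, 5, 10 and 15 years as far as follow-up supports. One minus Kaplan-Meier should not be used: at an event hazard of 0.5% and death of 2% a year it gives 7.2% against a true 6.3%.
- Events per 100 patient-years with an exact 95% CI.

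If RCR positivity is included, censor at the last RCR test. Section 7.6.2 lets sampling stop by rule, so last contact would credit untested time. Do not extend the table to all-cause late neurologic events without first checking ascertainment: Table 3 places Grade III-V neurologic events in the SAE row, where collection regardless of cause ends at 180 days after BPX-501 or 30 days after rimiducid. Keep number (%) for the early all-cause AE and SAE windows.

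The cost is analysis text and one extra table, with no new visits. The intervals will be wide: for 5 events in 175 patients, the exact 95% interval for the simple proportion already runs from about 0.9% to 6.5%.

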##### **10.4.6.2 Deaths, SAEs, and AEs Leading to Treatment Discontinuation**

SAEs, events leading to death, and AEs leading to treatment discontinuation will be summarized overall as well as by primary system organ class and preferred term.

#### **10.5 Reporting of Deviations to the Protocol**

All the deviations to the protocol will be described and justified in a separate form.

### **11 ETHICAL ISSUES/CONSIDERATIONS**

#### **11.1 Institutional and Ethical Review**

The study will be conducted according to the ethical principles of the declaration of Helsinki, the ICH-GCP Guidelines, the EU Clinical Trial Directive (2001/120/EG), Italian Ministry of Health

(decree of July 15, 1997), Saudi Food and Drug Authority, FDA and other international regulatory agencies.

## **11.2 Investigator's Responsibilities**

Any investigator or co-investigator who signed this protocol agrees to carry out this research in accordance with the protocol approved by the ethical committee, GCP and regulatory requirements. Study personnel involved in conducting this trial will be qualified by education, training, and experience to perform their respective task(s). The PI has the right to prematurely discontinue the study for significant efficacy or safety problems and will notify the co-investigators in writing, as well as the ethics committees and the competent authorities according to law and regulations.

### **11.2.1 Patient Informed Consent**

The patient or parents/legal guardians are to be informed both in writing and verbally by the investigating physician. The patient and his/her parents/guardians must be given ample opportunity to decide whether or not to participate in this study and to ask questions concerning this. It must also be made clear to the patient that he/she can withdraw from the study at any time without giving reasons and that he/she will not be in any way disadvantaged by this. Assent will be documented as required by the IRB or the EC. The informing physician, the patient or guardian must each personally date and sign an informed consent form with a declaration on data privacy. Any informed consent will be part of the investigator's file and retained with it. The patient will retain a copy of the patient information.

### **11.2.2 Data Management and Storage**

The investigator will organize the storage of the identification codes of the patients for at least 15 years after the end of the study. The files of the patients (medical records) and other original data will be kept for a minimum period of 15 years. Relevant parts of those records specific to support the traceability of BPX-501 from donor to recipient will be retained as applicable by the investigator, manufacturer and Sponsor per local requirement.

## Appendix A: Chronic GVHD Grading Scale and Assessment

### Appendix A.1: NIH Consensus Grading Chronic GVHD

		SCORE 0	SCORE 1	SCORE 2	SCORE 3
PERFORMANCE SCORE:	KPS ECOG LPS	 Asymptomatic and fully active (ECOG 0; KPS or LPS 100%)	 Symptomatic, fully ambulatory, restricted only in physically strenuous activity (ECOG 1, KPS or LPS 80-90%)	 Symptomatic, ambulatory, capable of self-care, >50% of waking hours out of bed (ECOG 2, KPS or LPS 60-70%)	 Symptomatic, limited self-care, >50% of waking hours in bed (ECOG 3-4, KPS or LPS <60%)
SKIN Clinical features:		 No Symptoms	 <18% BSA with disease signs but NO sclerotic features	 19-50% BSA OR involvement with superficial sclerotic features "not hidebound" (able to pinch)	 >50% BSA OR deep sclerotic features "hidebound" (unable to pinch) OR impaired mobility, ulceration or severe pruritus
		 Maculopapular rash			
		 Lichen planus-like features			
		 Papulosquamous lesions or ichthyosis			
		 Hyperpigmentation			
		 Hypopigmentation			
		 Keratosis pilaris			
		 Erythema			
		 Erythroderma			
		 Poikiloderma			
		 Sclerotic features			
		 Pruritus			
		 Hair involvement			
		 Nail involvement			
% BSA involved		 [ ]			
MOUTH		 No symptoms	 Mild symptoms with disease signs but not limiting oral intake significantly	 Moderate symptoms with disease signs with partial limitation of oral intake	 Severe symptoms with disease signs on examination with major limitation of oral intake
EYES		 No symptoms	 Mild dry eye symptoms not affecting ADL (requiring eyedrops $\leq 3$ x per day) OR asymptomatic signs of keratoconjunctivitis sicca	 Moderate dry eye symptoms partially affecting ADL (requiring drops $> 3$ x per day or punctal plugs), WITHOUT vision impairment	 Severe dry eye symptoms significantly affecting ADL (special eyewear to relieve pain) OR unable to work because of ocular symptoms OR loss of vision caused by keratoconjunctivitis sicca
GI TRACT		 No symptoms	 Symptoms such as dysphagia, anorexia, nausea, vomiting, abdominal pain or diarrhea without significant weight loss (<5%)	 Symptoms associated with mild to moderate weight loss (5-15%)	 Symptoms associated with significant weight loss $>15\%$ , requires nutritional supplement for most calorie needs OR esophageal dilation
LIVER		 Normal LFT	 Elevated Bilirubin, AP*, AST or ALT $<2 \times$ ULN	 Bilirubin $>3$ mg/dl or Bilirubin, enzymes 2-5 $\times$ ULN	 Bilirubin or enzymes $> 5 \times$ ULN

## Appendix A.1 NIH Consensus Grading Chronic GVHD (cont)

	SCORE 0	SCORE 1	SCORE 2	SCORE 3
LUNGS†	 No symptoms	 Mild symptoms (shortness of breath after climbing one flight of steps)	 Moderate symptoms (shortness of breath after walking on flat ground)	 Severe symptoms (shortness of breath at rest; requiring O 2 )
FEV1 				
DLCO 	 FEV1 > 80% OR LFS=2	 FEV1 60-79% OR LFS 3-5	 FEV1 40-59% OR LFS 6-9	 FEV1 ≤ 39% OR LFS 10-12
JOINTS AND FASCIA	 No symptoms	 Mild tightness of arms or legs, normal or mild decreased range of motion (ROM) AND not affecting ADL	 Tightness of arms or legs OR joint contractures, erythema thought due to fasciitis, moderate decrease ROM AND mild to moderate limitation of ADL	 Contractures WITH significant decrease of ROM AND significant limitation of ADL (unable to tie shoes, button shirts, dress self etc.)
GENITAL TRACT	 No symptoms	 Symptomatic with mild signs on exam AND no effect on coitus and minimal discomfort with gynecologic exam	 Symptomatic with moderate signs on exam AND with mild dyspareunia or discomfort with gynecologic exam	 Symptomatic WITH advanced signs (stricture, labial agglutination or severe ulceration) AND severe pain with coitus or inability to insert vaginal speculum

**Other indicators, clinical manifestations or complications related to chronic GVHD (check all that apply and assign a score to its severity (0-3) based on its functional impact where applicable (none – 0,mild -1, moderate -2, severe – 3))**

Esophageal stricture or web \_\_\_\_\_ Pericardial Effusion \_\_\_\_\_ Pleural Effusion(s) \_\_\_\_\_  
 Ascites (serositis) \_\_\_\_\_ Nephrotic syndrome \_\_\_\_\_ Peripheral Neuropathy \_\_\_\_\_  
 Myasthenia Gravis \_\_\_\_\_ Cardiomyopathy \_\_\_\_\_ Eosinophilia > 500/ $\mu$ l \_\_\_\_\_  
 Polymyositis \_\_\_\_\_ Cardiac conduction defects \_\_\_\_\_ Coronary artery involvement \_\_\_\_\_  
 Platelets <100,000/ $\mu$ l \_\_\_\_\_ Progressive onset \_\_\_\_\_

**OTHERS:** Specify: \_\_\_\_\_

**Global scoring of cGVHD**

Number of Organs	Mild cGVHD	Moderate cGVHD	Severe cGVHD
1	Score 1	Score 2	Score 3
2	Score 1	Score 2	Score 3
3		Score 1	Score 3
Lung involvement		Score 1	Score 2

Mild cGVHD = 1 or 2 organs involved (except for lung) with maximum score of 1

Moderate cGVHD = lung score of 1 or 3 organs with score of 1 or at least 1 organ with score of 2

Severe cGVHD = lung score of 2 or score of 3 in any organ.

## Appendix A.2: Response Determination for Chronic GvHD

Response Determination for Chronic GVHD Clinical Trials based on Clinician Assessments

Organ	Complete Response	Partial Response	Progression
Skin	NIH Skin Score 0 after previous involvement	Decrease in NIH Skin Score by 1 or more points	Increase in NIH Skin Score by 1 or more points, except 0 to 1
Eyes	NIH Eye Score 0 after previous involvement	Decrease in NIH Eye Score by 1 or more points	Increase in NIH Eye Score by 1 or more points, except 0 to 1
Mouth	NIH Modified OMRS 0 after previous involvement	Decrease in NIH Modified OMRS of 2 or more points	Increase in NIH Modified OMRS of 2 or more points
Esophagus	NIH Esophagus Score 0 after previous involvement	Decrease in NIH Esophagus Score by 1 or more points	Increase in NIH Esophagus Score by 1 or more points, except 0 to 1
Upper GI	NIH Upper GI Score 0 after previous involvement	Decrease in NIH Upper GI Score by 1 or more points	Increase in NIH Upper GI Score by 1 or more points, except 0 to 1
Lower GI	NIH Lower GI Score 0 after previous involvement	Decrease in NIH Lower GI Score by 1 or more points	Increase in NIH Lower GI Score by 1 or more points, except from 0 to 1
Liver	Normal ALT, alkaline phosphatase, and Total bilirubin after previous elevation of 1 or more	Decrease by 50%	Increase by 2 × ULN
Lungs	
 
- Normal %FEV1 after previous involvement
 
- If PFTs not available, NIH Lung Symptom Score 0 after previous involvement
 
	
 
- Increase by 10% predicted absolute value of %FEV1
 
- If PFTs not available, decrease in NIH Lung Symptom Score by 1 or more points
 
	
 
- Decrease by 10% predicted absolute value of %FEV1
 
- If PFTs not available, increase in NIH Lung Symptom Score by 1 or more points, except 0 to 1
 

Joints and fascia	Both NIH Joint and Fascia Score 0 and P-ROM score 25 after previous involvement by at least 1 measure	Decrease in NIH Joint and Fascia Score by 1 or more points or increase in P-ROM score by 1 point for any site	Increase in NIH Joint and Fascia Score by 1 or more points or decrease in P-ROM score by 1 point for any site
Global	Clinician overall severity score 0	Clinician overall severity score decreases by 2 or more points on a 0-10 scale	Clinician overall severity score increases by 2 or more points on a 0-10 scale

ULN indicates upper limit of normal.

